7.3 Criteria for treatment withdrawal

The patient may withdraw the informed consent and stop treatment at any time during the study, for any reason. The investigators and medical monitors may discontinue treatment for reasons of safety and/or lack of compliance, as detailed below. These patients will attend the follow-up safety visit. Patients who discontinue treatment will be followed up to determine radiological progression, subsequent neuroendocrine tumour treatments and survival.

Treatment withdrawal due to adverse events or safety reasons:

- Any unacceptable adverse event that cannot be appropriately managed by medical intervention or which, in the opinion of the investigator or the clinical monitor, poses excessive risk for the patient if the current dose is continued.
- Any unacceptable toxicity according to the protocol (see section 6.3. Safety assessment. Titration of the Study Drug.)
- Disease progression based on protocol criteria.
- Patients who, in the opinion of the investigator or clinical monitor, clearly fail to comply with the requirements of the protocol.
- Patient's absence from follow-up.
- Administration of chemotherapy or immunotherapy not envisaged by the protocol but that, in the opinion of medical staff, is required by the patient.
- Study ended by GETNE
- Patients who experience a treatment delay greater than 4 weeks will discontinue treatment and enter the follow-up phase, unless there is an obvious clinical benefit in the opinion of the investigator and after discussing it with GETNE [REDACTED]
- Whenever possible, after permanent treatment discontinuation, the patient should continue with the follow-up assessments as scheduled after the last treatment dose received. Any permanent treatment discontinuation must be recorded in the eCRF.

8. METHODOLOGY

8.1. Translational Section. Determination of Biomarkers.

Sample Collection

Tumour block collection

A paraffin-embedded tumour block will be requested and sent to [REDACTED] for the hypoxia marker expression study.

Collection of peripheral blood samples

10 ml of peripheral blood will be taken from each patient during the baseline visit and placed in EDTA tubes, to be sent to the Spanish National Cancer Research Centre for polymorphism study.

Handling and storage of samples

Tumour block

The paraffin blocks will be stored at room temperature under routine site conditions after the patient has signed the informed consent form, at which point they will be sent to the reference site.

Peripheral blood samples

The blood samples will be stored at -20 °C from the moment of extraction, and will be sent periodically to the reference site.

Sample shipping

Tumour block

The paraffin blocks will be sent with the periodic deliveries at room temperature (< 25 °C).

Peripheral blood samples

The blood samples will be sent all together and correctly identified in dry ice to the reference site.

Centralised receipt of samples

The paraffin-embedded tumour samples will be received by [REDACTED]

The samples will be received from Monday to Friday, from 08:00 to 15:00.

Peripheral blood samples will be received by [REDACTED] for the attention of:

The samples will be received from Monday to Friday, from 08:00 to 15:00.

Sample processing

Tumour block

The paraffin blocks will be analysed by specialised pathologists as they are received. The expression of hypoxia-related proteins such as CAIX, HIF2A/HIF-1alpha, VEGF, CYP2W1 and c-myc will be assessed centrally and retrospectively in immunohistochemistry.

Peripheral blood:

DNA will be isolated from the peripheral blood, following the instructions of the “FlexiGene DNA kit” (Qiagen), and the concentration of the DNA extracted will be quantitated by the “PicoGreen® dsDNA quantitation reagent” (Invitrogen). The DNA will be stored at -20 °C until genotyping.

Genotyping will be carried out by standard techniques (for example, “TaqMan Probes”, or “KASPar SNP Genotyping System”) using 15 ng of genomic DNA. Fluorescence detection and allele assignment will be performed using the “7900HT Detection System” by Applied Biosystems. The results obtained will be used to create a genetic database, which will collect the genotypes of each patient enrolled in the study.

The list of polymorphisms to genotype includes variants in the following candidate genes:

VEGFR2 (rs2305948 and rs1870377), *VEGFR3* (rs307826), *IL8* (rs1126647), *CYP3A4* (rs35599367 and [rs67666821](#)), *CYP3A5* (rs776746), *ABCB1* (rs1045642, rs1128503 and rs2032582), *POR* (rs1057868 and c.1705_1706insG). If a polymorphism of particular relevance and related to the effectiveness of sunitinib or TH-302 appears in the literature as the study progresses, its inclusion in the study could be considered.

The procedure for coding and shipping samples is detailed in a separate document.

9. STATISTICAL ANALYSIS

9.1. *Descriptive Analysis*

The descriptive analysis of patient characteristics will include demographic data, disease-specific data and prior treatments. Qualitative data will be described with absolute frequencies and corresponding percentages. Quantitative data will be studied using the mean \pm standard deviation, median, minimum and maximum values. The response percentages will be estimated using confidence intervals of 95%. In the safety analysis, adverse events will be specified according to the maximum grade described at the discretion of the investigator and defined by NCI-CTCAE, version 4.0 (see section 10.2.3.), including adverse events described from treatment initiation until 28 days following its completion.

The following safety analysis data will be presented:

- Temporary and permanent treatment discontinuations due to an adverse event.
- Deaths.
- Adverse Events (AEs) and Serious Adverse Events (SAEs).
- Hospitalisations.
- Use of concomitant medication and growth factors.

9.2. *Inferential Analysis*

The objective response rate corresponding to the percentage of patients in which there is confirmation of a complete response (CR) or a partial response (PR) according to RECIST criteria, in relation to the total analysis population, will include a confidence interval of 95%. The association between the marker expression profiles analysed in plasma and in tumour tissue for treatment response (yes/no) will be assessed using logistic regression models and univariate and multivariate Cox regression, establishing the corresponding *hazard ratio* and confidence interval at 95%. The predictive value (of genetic biomarkers, in plasma and tumour tissue) of each model will be estimated using an area under the ROC curve.

The survival analyses will be performed using the Kaplan-Meier method presented with the corresponding graph, as well as by Cox regression analysis to obtain the *hazard ratios* and confidence intervals for the associations. For patients without documented progression or death at the time of analysis, the PFS will be censored at the last date of tumour assessment. For patients who have not died at the time of analysis, the OS will be censored.

All statistical tests are bilateral, two-tailed tests, and all values with $p < 0.05$ will be considered significant.

10. ASSESSMENT CRITERIA

10.1. Efficacy Assessment

Objective response rate (ORR)

This will be assessed according to RECIST version 1.1 criteria, to be performed every 8 weeks, regardless of treatment delays caused by treatment toxicity.

The ORR is defined as the percentage of patients in which there is confirmation of a complete response (CR) or a partial response (PR) according to RECIST criteria, in relation to the total analysis population.

A response is confirmed for patients in whom the response persists in an imaging test repeated ≥ 4 weeks after initial documentation of response.

Progression-free survival (PFS)

This is defined as the time between the start of study treatment to the date of first objective evidence of radiological progression or patient death from any cause; whichever comes first.

Time to progression (TTP)

This is defined as the time between the start of study treatment to the date of first objective evidence of radiological progression.

Response duration (RD)

This is defined as the time between the first recorded objective response (CR or PR), which is subsequently confirmed, to the first objective evidence of radiological progression or death from any cause.

RD will only be calculated in the subgroup of patients with objective response (CR + PR).

Overall survival (OS)

This is defined as the time between the start of study treatment to the date of death from any cause. If confirmation of death could not be obtained, survival will be censored with the date of the last visit at which time the patient was known to be alive.

Safety

See Safety Assessment section below.

Biomarkers:

They assess the correlation between radiological response and the patient's clinical course and the following expression levels:

A phase II trial to assess the activity and safety of TH-302 in combination with sunitinib in patients

- ENO1 (enolase 1) in plasma (it will be performed locally at the same time as chromogranin at each participating site)
- SNPs (single nucleotide polymorphisms) related to the activity and metabolism of sunitinib and TH-302 *VEGFR2* (rs2305948 and rs1870377), *VEGFR3* (rs307826), *IL8* (rs1126647), *CYP3A4* (rs35599367 and [rs67666821](#)), *CYP3A5* (rs776746), *ABCB1* (rs1045642, rs1128503 and rs2032582), *POR* (rs1057868 and c.1705_1706insG). If a polymorphism of particular relevance and related to the effectiveness of sunitinib or TH-302 appears in the literature as the study progresses, its inclusion in the study could be considered.
- Hypoxia markers related to paraffin-embedded tumour tissue (HIF1- α , CYP2W1 and c-Myc).

10.2 Safety Assessment

10.2.1 Safety Analysis

The safety period runs from the date of the signature of the informed consent form until 28 days after the last dose of the study drug. Safety will be evaluated according to adverse event reports, the frequency of treatment discontinuations due to adverse events, and laboratory or ECG tests. Descriptive analysis will be used.

10.2.2 Adverse Events

An adverse event is defined as any unwanted or unintended symptom, sign, disease or experience (including a clinically significant laboratory result of any grade according to the common terminology criteria for adverse events [*CTCAE*] of the National Cancer Institute, version 4.0) that emerges or worsens during the course of the study, whether related or not to the study drug.

The assessment of adverse events will include type (symptoms from the medical history, physical examination findings or laboratory/ECG/radiological/other diagnostic procedure abnormalities), prevalence, severity/seriousness, time and their link.

Examples of adverse events are the following:

- Deterioration (excluding mild fluctuations) of the nature, intensity, frequency, or duration of a pre-existing condition.
- Development of an intercurrent illness during the study.
- Development of symptoms that may or may not be associated with the use of a concomitant medication or the study drug.
- Injury or accidents: if a medical condition is known to have caused the injury or accident, both the medical condition as well as the accident should be recorded as two independent medical events (e.g., in the event of a fall caused by dizziness, both the “fall” and the “dizziness” must be recorded separately).

The following situations will not be classified as adverse events:

A phase II trial to assess the activity and safety of TH-302 in combination with sunitinib in patients

- Medical or surgical procedures (e.g., surgery, endoscopy, tooth extraction, transfusion). However, the disease precipitating the procedure is an adverse event.
- Pre-existing conditions or diseases present or detected prior to the first administration of the study drug that do not deteriorate.
- Circumstances in which no unwanted medical events manifest (e.g., hospitalisation for elective surgery, hospitalisations for social circumstances and/or convenience).

The relationship between the adverse event and the study drug:

The reasonable possibility of a link between the adverse event and the study drug will be determined. In cases where the study site investigator is unable to make an objective judgement, the opinion of the clinical monitor should be sought. The following definitions will be used:

- Not related: There is no possible relationship to the study drug. The temporal relationship between drug exposure and the start/evolution of the adverse event is unreasonable or incompatible, or a causal relationship to the study drug is implausible.
- Unlikely: If the study drug is deemed not to be reasonably related to the adverse event, but a causal relationship cannot be ruled out. Although the temporal relationship between exposure to the study drug and the start/evolution of the adverse event does not exclude causality, there is a clear alternative cause that is more likely to have caused the adverse event than the study drug.
- Possible: The causal relationship to the study drug is not clear. The temporal relationship between drug exposure and the start/evolution of the adverse event is reasonable or unknown, information regarding the discontinuation of exposure or re-exposure is unknown or ambiguous, and although there are no other potential causes, a causal relationship with the study drug does not seem likely.
- Likely: There is a high degree of certainty for the causal relationship between the study drug and the adverse event. The temporal relationship between drug exposure and the start/evolution of the adverse event is reasonable, the response is clinically compatible with discontinuation of exposure, other causes have been ruled out and the event must be conclusive from a pharmacological or phenomenological point of view, adopting a re-exposure procedure if necessary.
- Definite: The causal relationship is clear. The temporal relationship between drug exposure and the start/evolution of the adverse event is reasonable, the response is clinically compatible with discontinuation of exposure, other causes have been ruled out and the event must be pharmacologically or phenomenologically conclusive, adopting a re-exposure procedure if necessary.

For the purposes of expedited reporting, the categories “definite”, “probable” and “possible” will be considered related to the study medication, and the categories “improbable” and “not related” shall be considered unrelated to the study medication.

The site’s principal investigator, or the person delegated by said investigator, is responsible for determining the relationship of the adverse event to the study medication.

Recording and reporting of adverse events:

All adverse events experienced by patients, regardless of their relationship to the study drug, must be reported in full on the adverse event page of the case report form and in the patient’s medical record, adopting the appropriate medical terminology. The severity, the result and relationship to the study drug will be determined and documented in the case report form.

Should a patient discontinue the study drug due to an adverse event, this must be recorded in the case report form. In the event of patient death caused by disease progression, the data will be included in the efficacy analysis, unless the investigator feels that the event is related to the study medication. Adverse events will be monitored until they have been resolved, or until they have stabilised and/or reached a new baseline level. If an adverse event has not been resolved before the end of the study, the investigator and the medical monitor will perform a clinical assessment to determine whether its follow-up is justified.

The site investigator must record all directly observed adverse events and all adverse events that were spontaneously reported.

It should be noted that the intermittent or on-demand use of any medicine (and specifically any newly-prescribed medication) throughout the study could precipitate the onset of an adverse event that would have to be recorded on the case report form, both on the adverse event form as well as the concomitant medication form.

Adverse events will be recorded on the case report form from patient enrolment after the informed consent form has been signed, during the study treatment and 28 days following the end of treatment. During the long-term follow-up, following the 28-day period after the end of treatment, adverse events (AEs) related to the study treatment or procedures will be recorded, even after study completion, until stabilisation or until the outcome is known, unless the subject is documented as “lost to follow-up”. In addition, should the patient sign the informed consent form but not receive treatment, adverse events will be recorded that the investigator considers to be related to the study procedures.

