Through the study's principal investigator, the sponsor (GETNE) will assess the SAEs, taking into account the product safety reference documents, and will report, through the CRO, those SAEs that meet the expedited reporting criteria (serious, unexpected and related to the study medication) with the help of the monitor. The sponsor is responsible for notifying the competent authorities (Spanish Agency of Medicines and Medical Devices - AEMPS, central IEC, hospital IEC, competent bodies of the Autonomous Communities) and the principal investigators/institutions involved in the study, and this will be carried out within the time scales determined by current Spanish legislation. The maximum period for notification shall be 15 calendar days from the time the sponsor learns of the suspected adverse reaction. However, if the unexpected serious adverse reaction leads to the patient's death, or endangers the patient's life, the sponsor shall inform the AEMPS within 7 calendar days from the time it became aware of the situation. Said information shall be completed, as far as possible, within the following 8 calendar days.

All SAEs will undergo a follow-up until the following situations are reached:

- Event resolution
- Event stabilisation.
- Restoration of the baseline situation and, if available, a baseline value.
- The event can be attributed to products other than the study treatment or factors not related to the study.
- It is not possible to obtain further information.

All unresolved SAEs at the conclusion of the study must be followed up, to determine the end result.

SAEs will be recorded from the time the patient signs the informed consent form until the follow-up safety visit, 28 days after the last dose of the study drug, or until the start of administration of an investigational or medical drug, whichever comes first.

Fatal events (regardless of their relationship to the study drug) will be recorded as serious adverse events up to the follow-up safety visit (28 days after discontinuation of the study drug) or until the start of further treatment, whichever comes first. Fatal events that occur after the follow-up safety visit (28 days after discontinuation of the study drug) or upon initiation of an investigational or medical drug, whichever comes first, will not be recorded as serious adverse events but will be recorded on the corresponding case report form.

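### No category on the adverse-event causality scale fits an event with plausible timing and a competing cause no more likely than the drug, because *Possible* is worded as having no other potential causes

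*Protocol*

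**What the plan says.** Protocol section 10.2.2 asks the site to judge whether a link with study drug is reasonably possible and introduces its scale with "The following definitions will be used". The five categories are:

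- *Not related*: "There is no possible relationship to the study drug", because timing is incompatible or causation implausible.
- *Unlikely*: timing does not exclude causality, but "there is a clear alternative cause that is more likely to have caused the adverse event than the study drug".
- *Possible*: timing is reasonable or unknown, information on stopping or re-exposure is missing or ambiguous, and "although there are no other potential causes, a causal relationship with the study drug does not seem likely".
- *Likely*: timing is reasonable, the course after stopping is compatible, and "other causes have been ruled out and the event must be conclusive from a pharmacological or phenomenological point of view".
- *Definite*: nearly the same criteria as *Likely*, again with other causes ruled out.

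The same section then sets the cut for expedited reporting. Definite, probable and possible "will be considered related to the study medication, and the categories" improbable and not related count as unrelated. The site's principal investigator or delegate determines the relationship.

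Section 10.2.4 makes relatedness one of three conditions for expedited reporting: "serious, unexpected and related to the study medication". Section 10.2.2 also says that in long-term follow-up, once 28 days have passed since the end of treatment, "adverse events (AEs) related to the study treatment or procedures will be recorded, even after study completion".

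**The concern.** A causality scale needs a place for the event that might be due to the drug and might be due to something else. That is normally the role of the middle category. Here the middle category is worded to exclude other potential causes, and the categories on either side do not pick up what it leaves out.

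Such events are to be expected in this trial. Patients have advanced disease, receive two study drugs, and may take somatostatin analogues and other treatment (section 6.3.6). The boundary between *Possible* and *Unlikely* is also the boundary between related and unrelated. If sites resolve the gap differently, like events will fall on different sides of it. If they resolve it towards *Unlikely*, a serious unexpected event could fail the relatedness condition for expedited reporting.

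**Working it through.** No figure is stated or disputed, so the check is logical: apply each definition to one test event, then see where the result is used.

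**Test event.** Timing is reasonable, the course after stopping is ambiguous, and there is a competing cause (the tumour or a concomitant drug) no more likely than the study drug.

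| Category | Condition that decides | Met? |
|---|---|---|
| *Not related* | incompatible timing or implausible causation | No: timing is reasonable and causation plausible |
| *Unlikely* | clear alternative, more likely than the drug | No: the alternative is not more likely |
| *Possible* | no other potential causes | No: there is one |
| *Likely* | other causes ruled out | No |
| *Definite* | other causes ruled out | No |

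Result: 0 of 5 categories fit. A clearer course after stopping would not help, because *Likely* and *Definite* would still fail on the competing cause.

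**Extent of the gap.** With plausible timing there are four cases:

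- (a) A clear alternative, more likely than the drug: *Unlikely*, counted as unrelated if improbable is read as *Unlikely*.
- (b) An alternative as likely as the drug, or less likely: no category.
- (c) No other cause, but the drug does not seem likely: *Possible*, counted as related.
- (d) Other causes ruled out and the event conclusive: *Likely* or *Definite*, both on the related side if probable is read as *Likely*.

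The gap is case (b) only.

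**Labels.** The scale has *Likely* and *Unlikely*; the reporting rule has probable and improbable. The intended pairing is easy to guess, but the rule never assigns the scale's own two labels to either side.

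**Where the cut is used.**

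- Expedited reporting: directly, through sections 10.2.2 and 10.2.4.
- Recording after the 28-day window (section 10.2.2): by inference. That sentence says related without citing the five categories, but no other definition of relatedness is given.
- Planned safety analysis: not used. Protocol sections 9.1 and 10.2.1 and SAP sections 1.5.5.1, 1.5.5.4 and 2.8 call for events by maximum grade, serious events, deaths, hospitalisations, discontinuations, laboratory and ECG results and concomitant medication. SAP Table 34 is by grade with no relatedness column.

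Other places, such as the titration tables in section 6.3.4, use words like drug-related without reference to this scale. I draw no consequence from them.

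**The case against.** The strongest reply is that the text around the definitions steers case (b) to the right place. The general standard in section 10.2.2 is a reasonable possibility of a link. *Possible* opens by saying that the causal relationship is not clear, whereas *Unlikely* opens by saying that the drug is not reasonably related. A sensible investigator may therefore code the test event as *Possible*, and an investigator who cannot decide is told to ask the clinical monitor. A strictly literal reader could not use *Unlikely* either, so drift in that direction is a prediction about behaviour and not something the text dictates.

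Much of this stands. It means that coding would vary with how a site reads the definition, not that it would be uniformly wrong. It does not close the gap. The opening sentence and the stated criterion of *Possible* point different ways for this event, and the monitor is consulted only when the investigator cannot judge. An investigator who confidently chooses *Unlikely* never reaches that step.

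A second reply is that section 10.2.4 has serious events notified within 24 hours whether or not they are related, after which the sponsor assesses them. This also stands and is the main reason the consequence is limited. Two limits remain. Routine recording of serious events ends 28 days after the last dose, or earlier if another drug is started. And the protocol makes the site responsible for the causality call without saying that the sponsor may change it.

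A reader might infer more than the documents support:

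- That the safety endpoint is compromised. No planned safety output uses relatedness, and events are counted whether related or not.
- That every event with another possible cause lacks a category. *Unlikely* does cover a clear, more likely alternative.
- That calling *Possible* not likely while counting it as related is a contradiction. It can be read as falling short of *Likely*, so the sounder point is the exclusion of other causes.
- That the near-identical *Likely* and *Definite* distort the split. Both are on the related side, so their overlap does not move it.

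**Conclusion.** The point holds as a wording defect in an operative rule. As written, none of the five categories accepts an event with plausible timing and a competing cause of similar or lesser weight. Because *Unlikely* is the only category that expressly allows an alternative cause, the more probable error is to class such an event as unrelated, though the documents do not establish that sites will do so.

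The consequence reaches the relatedness condition for expedited reporting and, assuming the same scale governs that sentence, which events are recorded after 28 days. It touches no endpoint, estimate or planned table. The number of affected events cannot be derived from the documents. The conclusion rests on reading the criteria as conditions to be met; CRF labels and instructions, which are not available here, might already resolve it.

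**What to change.** Amend section 10.2.2 as follows:

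- Reword *Possible*: timing reasonable or unknown; information on stopping or re-exposure missing or ambiguous; other potential causes may exist or cannot be excluded; and a causal relationship is a reasonable possibility. This matches the standard stated earlier in the same section.
- Keep *Unlikely* for a clear alternative that is more likely than the drug.
- State the reporting rule in the scale's own labels: *Definite*, *Likely* and *Possible* are related; *Unlikely* and *Not related* are unrelated. Check that the CRF uses the same five labels.
- Say whether the same cut decides which events are recorded after the 28-day window.

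Separating or merging *Likely* and *Definite* is optional tidying and does not change the cut.

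The cost is a wording amendment and a CRF label check. The downside is that somewhat more events may be classed as related and reported.

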#### Progression-free survival (PFS)

This is defined as the time between the start of study treatment to the date of first objective evidence of radiological progression or patient death from any cause; whichever comes first.

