### Overall survival (OS)

This is defined as the time between the start of study treatment to the date of death from any cause.

If confirmation of death could not be obtained, survival will be censored with the date of the last visit at which time the patient was known to be alive.

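### Protocol 10.2.2 makes a progression death's place in the efficacy analysis depend on the investigator's causality opinion, which conflicts with the any-cause definitions of PFS, response duration and OS

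*Protocol*

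**What the plan says.** The sentence is in protocol 10.2.2, under the recording and reporting of adverse events. It opens with a condition, limiting it to deaths that disease progression has caused, and then gives a rule with an exception: "the data will be included in the efficacy analysis, unless the investigator feels that the event is related to the study medication". Neither document says what happens to an excepted death: whether it is censored, whether the patient is dropped, or whether it is only filed elsewhere.

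The endpoint definitions contain no such exception:

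- **PFS.** Protocol 10.1 runs to the "date of first objective evidence of radiological progression or patient death from any cause; whichever comes first". The SAP's PFS definition (1.5.2) likewise ends at "radiological progression or patient death from any cause; whichever comes first".
- **Response duration.** Protocol 10.1 runs from first response "to the first objective evidence of radiological progression or death from any cause". SAP 1.5.2 says the same.
- **OS.** Protocol 10.1 takes "the time between the start of study treatment to the date of death from any cause", and SAP 1.5.2 repeats it.

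Protocol 9.2 and SAP 1.5.5.3 censor PFS only in patients with neither documented progression nor death, and censor OS only in patients who have not died. SAP 1.5.1.1 defines the total analysis population by the eligibility criteria alone.

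**The concern.** A death that 10.1 and the SAP count as an event could be left out under 10.2.2 because the investigator thought the drug contributed. The trial is single-arm and open-label. Relatedness is judged by the site investigator or a delegate, and for expedited reporting 10.2.2 treats even a possible link as related. Whether such a death counted would then rest on an unblinded opinion formed after the outcome was known.

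Deaths in which the combination may have played a part are ones that survival estimates should count against it. Censoring them would be informative, and there is no control arm in which the same practice might offset it.

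**Working it through.** The documents give no figure on this point, so there is nothing to reproduce. The check compares the texts, works out which endpoints could move, and then illustrates the size under stated assumptions.

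**1. Can both rules be followed?** Take a patient who dies of progression in a way the investigator considers related to study medication. Under 10.1 and SAP 1.5.2 this is an OS event, and also a PFS event if no radiological progression was documented earlier. Under a literal reading of 10.2.2 the data are not in the efficacy analysis. The two cannot both be applied. Nor do the censoring rules reconcile them, since the patient has died and so does not qualify for censoring.

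**2. Which endpoints could move?**

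- *Radiological progression documented before death* (likely for a progression death): PFS already has its event at the progression date, as does response duration in a responder. Leaving the death uncounted changes neither. Only OS can move.
- *Death before a scan documents progression:* this is possible because progression must be radiological (10.1) and scans are 8 weeks apart, plus or minus one week (11.4, 11.6). Death is then the event for PFS, and for response duration in a responder, so these can move along with OS.

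**3. Illustration for 12-month OS.** Inputs: N = 43 (protocol 5.4) and one-year survival of 81.1% in the cited phase II sunitinib study (protocol 3.3), assumed to apply here. Expected deaths are 43 × (1 − 0.811) = 8.1, taken as 8, with no other censoring before 12 months. The number k of excepted deaths is an assumption.

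| k | Patient removed: 35/(43 − k) | Death not counted: (35 + k)/43 |
|---|---|---|
| 0 | 35/43 = 81.4% | 35/43 = 81.4% |
| 1 | 35/42 = 83.3% | 36/43 = 83.7% |
| 2 | 35/41 = 85.4% | 37/43 = 86.0% |

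Censoring at the date of death gives a Kaplan-Meier estimate within these limits. It equals the first column if the excepted deaths come before all the others, and the second if they come after.

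**4. Illustration for median PFS.** This applies only to the second case in step 2. Assume exponential PFS with a median of 11.4 months (the sunitinib arm of the phase III study in protocol 3.3), and let q be the share of PFS events that are excepted deaths. Censoring them lowers the event hazard by the factor (1 − q), so the apparent median is 11.4/(1 − q):

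- q = 0: 11.4 months
- q = 2%: 11.4/0.98 = 11.6
- q = 5%: 11.4/0.95 = 12.0
- q = 10%: 11.4/0.90 = 12.7
- q = 20%: 11.4/0.80 = 14.25

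A Kaplan-Meier simulation (43 patients, 4,000 runs, uniform censoring between 20 and 44 months) gave 11.6, 12.0, 12.8 and 14.2 months for q = 2, 5, 10 and 20%. If the patients are dropped instead, with such deaths spread evenly over time, the simulated medians are 11.2, 11.4, 11.6 and 12.0, against 11.3 to 11.5 with every death counted. The PFS effect therefore depends on how the exception is applied, which the documents do not say. No figure was computed for response duration.

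**The case against.** The strongest reply is that this is a recording instruction. It sits between instructions on CRF entry and on adverse-event follow-up. Section 10.2.4 has similar wording, in which an event is not reported within 24 hours but is entered in the CRF and analysed as an objective. On that reading, a progression death is captured as an efficacy outcome unless drug-related, in which case it is handled as a safety event. The text that governs the analysis is also clear: the SAP's definitions, censoring rules and eligibility-based population contain no exception. SAP Table 22 counts deaths without prior progression and Table 26 counts deaths, neither split by relatedness.

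Most of this stands, and it limits the point to a risk if 10.2.2 is applied. It does not make the sentence harmless. The sentence names the efficacy analysis rather than a form or a reporting deadline, and the SAP does not say that it overrides it. Sorting deaths by relatedness also fits poorly with the protocol's own safety rules: 10.2.2 requires every adverse event to be reported whatever its relationship to the drug, and 10.2.4 does the same for fatal events up to the 28-day safety visit.

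A reader might infer that every death judged drug-related is removed from the efficacy analysis. The text does not say so. The exception is tied to deaths caused by disease progression; for a toxic death without progression, exclusion is at most implied. A reader might also infer that PFS, response duration and OS are all biased upward. Step 2 of the working shows that PFS and response duration do not move when radiological progression was documented first.

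**Conclusion.** The inconsistency is real and should be corrected, but it is narrow. If the 10.2.2 sentence were applied, OS would be exposed whenever a death is excepted, and PFS and response duration only where death comes before documented radiological progression. Under the assumptions of the OS illustration, one excepted death adds about 1.9 to 2.3 percentage points to 12-month OS (83.3 − 81.4 and 83.7 − 81.4), and two add about 4.0 to 4.6 (85.4 − 81.4 and 86.0 − 81.4). With none there is no effect. How many deaths would be both caused by progression and judged drug-related is unknown, and the category may be small.

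The affected endpoints are secondary. The primary ORR is defined by confirmed response over an eligibility-based population, and the Simon rules count responders, so neither is affected. Sample size, alpha and power do not change.

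**What to change.** Replace the sentence in protocol 10.2.2 with: *Every death, whatever its cause or relationship to study medication, is an event for OS, and for PFS and response duration if progression has not been documented earlier; the relatedness judgement affects only AE/SAE classification.*

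The SAP already counts death from any cause, so repeating the sentence in SAP 1.5.2 is optional. The cost is one protocol sentence. The downside is that survival figures may be slightly less favourable than if the exception were applied.
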